PICC	Peripherally inserted central catheter

Study Aim

Currently there is little international or UK consensus regarding the route or duration of antibiotic treatment for acute osteomyelitis (OM)/septic arthritis (SA) in children. Data regarding paediatric bone and joint infections in the UK are scarce and outdated. This service evaluation will be used to:

1. Assess current case load, disease spectrum & clinical practice in the diagnosis & treatment of OM/SA in secondary & tertiary UK care
2. Determine whether a randomised controlled trial to investigate shorter duration of intravenous antibiotic therapy for bone and joint infections in children is feasible in the future.

This will be achieved in conjunction with a future component of the study (analysis plan of which not included in this document) obtaining qualitative & quantitative data on:

- a) willingness of clinicians to randomise to proposed protocol
- b) willingness of patients & parents to be randomized
- c) number of patients seen;
- d) clinical stakeholder & consumer perception of relevant outcomes

Study Design

This service evaluation is a descriptive study, examining routinely collected clinical data for all eligible paediatric cases of OM and SA presenting at participating tertiary and secondary healthcare centres over a minimum of a 6 months period.

Participating centres

All Tertiary and Secondary centres routinely treating cases of OM or SA from across England will be invited to participate in this national service evaluation. They will record data on all cases accrued over at least a 6 month period.

Participant selection criteria

All eligible patients presenting to participating centres with a diagnosis of bone and joint infection will be enrolled with no maximum, and data will be entered into a web based database.

Inclusion Criteria

All children from birth to 16 years with a clinical diagnosis of osteomyelitis or septic arthritis admitted to participating hospitals from home, or referred from another centre.

Exclusion Criteria

Patients whose parents have specifically requested for their child not to be included in the study.

Participant identification and recruitment

Posters displayed on admitting wards notify parents and patients that the centre is participating in a national service evaluation of children's bone and joint infections. Parents will have the opportunity to inform a member of their child's care team if they do not want their child's information entered into the database.

Sample size calculations

The study is funded to enable a maximum of 1,000 cases of OM or SA to be entered into the database. In order to get an accurate national evaluation, all participating centres will be asked to record cases for at least six months. It is estimated that at least 500 cases will be accrued by around 50 centres over a 6-12 month period. All eligible cases at participating centres will be recorded.

Data Collection

We will record demographic details and details of hospitalisation(s) including transfers between hospitals; type and site of disease; routine haematology, biochemistry and microbiology; radiological procedures; surgical procedures; length of IV therapy; antimicrobials used, route and duration; reason/criteria; used for oral switch (if any); and clinical outcomes at 3 months.

These data are to be collected from the patients' clinical notes. Training will be provided for teams at participating centres. The study will use a password protected web based data collection form that can be accessed at all participating hospitals.

Study Objectives

The study has three major objectives:

1. What are the clinical, biochemical and radiological criteria used by UK paediatricians / orthopaedic surgeons / radiologists to diagnose osteomyelitis?
2. What is the range of durations of intravenous and oral antibiotics used to treat osteomyelitis? What factors affect durations (e.g. surgery / blood tests / microbiology results).
3. What are the rates of treatment failures / complications for different:
 - (a) Antibiotic regimes used at participating centres?
 - (b) Surgery types used at participating centres?

and what actions were taken following a complication at participating centres?

These objectives are broken down into further sub-objectives:

- 1A:** Describe the study sample: demographics; past medical history; presenting limbs/joints affected; and diagnosis types aiming to identify factors predisposing children to bone and joint infections. Describe pre-presentation variables that affect drug choice, dosage and duration, in particular age, allergies and co-morbidities.
- 1B:** Describe the clinical time-line for diagnosis: summarising the number of days from presentation when key clinical actions (1st imaging, surgery and initiation of IV antibiotics) occur.
- 1C:** Describe the surgical procedures carried out prior to diagnosis.
- 1D:** Summarise the types of microbiological tests carried out and the types of samples taken. Specifically, find the proportion of centres that are performing PCR tests, and testing for Panton-Valentine Leukocidin producing *Staphylococcus aureus*.
Calculate the proportion of children testing positive for: at least one micro-organism; and each specific micro-organism (using conventional techniques, ie not PCR).
- 1E:** Describe the combinations of blood-tests carried out at presentation and summarise the test results. Find the proportion of children with elevated results for each blood-test type at presentation (results above centre-specific normal ranges), and the proportion of children with CRP_{max} occurring at presentation. Describe the types of samples.
- 1F:** Summarise CRP_{max} by age-group and micro-organisms detected.
- 1G:** Describe the imaging methods routinely used to aid diagnosis. What proportions of each method gave an abnormal result..
- 2A:** Describe the clinical time-line for antibiotic treatment (specifically when antibiotics are started) Describe the types of antibiotic regimes prescribed. Summarise the number of different antibiotics given as initial treatment, and the total number of different antibiotics patients receive over the durations of treatment by each route. Summarise the numbers of children being given different types of regime: early vs

normal length of time to oral switch; dosage – how many were given normal doses throughout; shortened vs standard length of time on antibiotics.

- 2B:** Describe the IV and oral antibiotics prescribed during hospital stay. For each antibiotic: which were prescribed at least once; which were part of the initial treatment; what was the average daily dose; with what frequency were doses given; and was the duration greater than 1 week. Were there differences in initial IV antibiotic prescriptions between secondary and tertiary site types; between children with and without penicillin allergy; and with and without sickle cell disease?
- 2C:** Describe the combinations of blood-tests carried out immediately prior to oral switch and summarise the test results. Calculate the average CRP at oral switch as a proportion CRP_{max} . Summarise blood test results over time: from presentation through to last test.
- 2D:** Describe the surgical procedures carried out post diagnosis but prior to discharge, i.e. therapeutic procedures. How many children had only one procedure, two procedures or more than two?
- 2E:** Summarise the length of time spent in hospital: from hospitalisation to discharge.
- [2F]: Summarise imaging carried out after initiation of IV, split by site type and image type. For each imaging type, identify cases that had at least one image carried out.
- 2G:** Describe the antibiotic regimes prescribed at discharge (drug, dose, frequency and duration). As part of this – what percentage went home on IV as opposed to oral?
- 2H:** Were discharge antibiotic regimes adhered to? Percentages of treatments shortened or changed post discharge, split by who made the decision: parent, hospital or GP. Describe the main reasons for non-adherence or change of regime post discharge.
- 3A:** Describe rates of different types of complication, and cross-tabulate with types of action taken.
- 3B:** Describe rates of Treatment Failure (Yes/No) and Any Complications (Yes/No) for different antibiotic regimes types. Measure associations between regime types and the two outcomes: Treatment Failure; and Any Complications.
- 3C:** Describe rates of Treatment Failure (Yes/No) and Any Complications (Yes/No) for different surgery types carried out post presentation. Measure associations between surgery types undertaken and the two outcomes: Treatment Failure; and Any Complications.

Description of the study population

Representativeness of cases accrued

The participating centres will be summarised and checked that they broadly represent all areas of the country. The numbers of cases withdrawn will be recorded.

Sample characteristics and initial categorisation of types of cases

The demographics of the sample (age, gender, medical history) will be described using summary statistics. Based on past medical history, cases will be categorised into four groups:

1. Simple cases
2. Complex cases
3. Current presentation due to infected implant or infected surgery from past orthopaedic surgery. (Subset of complex cases)
4. Misdiagnosed

Any children not falling into any of these categories will be excluded from the analysis.

Definitions

1. Simple cases

Children presenting with SA or OM for the first time, and with no chronic comorbidities. Specifically:

- No orthopaedic surgery 6 months prior to presentation on same limb/joint
- No chronic co-morbidities (sickle cell disease, known immunocompromise, indwelling central venous catheter or PICC, cystic fibrosis, or cerebral palsy).

2. Complex cases

Children presenting with SA or OM who already have a diagnosis of SA or OM and/or have chronic comorbidities, but who are not presenting because of an infected implant from previous orthopaedic surgery. Specifically:

- Not presenting because of an infected implant
- Any orthopaedic surgery in 6 months prior to presentation on same limb/joint
- Any chronic co-morbidities (sickle cell disease, known immunocompromise, indwelling central venous catheter or PICC, cystic fibrosis, or cerebral palsy).

3. Infected implants

Children presenting with SA or OM who already have a diagnosis of SA or OM and who are presenting because of an infected implant from previous orthopaedic surgery.

4. Incorrect diagnosis of SA/OM

Some children captured by the database were treated for SA/OM but were later found to have a different diagnosis.

Completeness of follow-up

Follow-up data are collected at a follow-up visit at around 3 months post discharge. The number lost to follow up will be reported and the reasons where known will be documented. Any deaths and their causes will be reported separately.

Study Outcomes

This study examines many measurements routinely made in the diagnosis, treatment, and aftercare of children with SA or OM. There are three areas of key interest: Diagnosis (Objective 1); Treatment (Objective 2); and Complications Arising and/or Treatment Failures (Objective 3). The key endpoints are:

Diagnosis:

- Bones and joints affected
- Time taken from first presentation to:
 1. Referral to hospital
 2. Having surgery
 3. Initiation of IV antibiotics [this time-point used also as a proxy for a diagnosis being made]
- Surgical procedures carried out prior to diagnosis
- Imaging types used (X-ray, CT scan, ultrasound, bone scan, MRI), and results obtained
- Diagnostic blood tests carried out (Hb, WBC, N, Plt, CRP, ESR) and their outcomes
- Microbiological tests carried out (presence of any of 8 named micro-organisms)

Antibiotic Treatment in and post hospital stay:

- Length of time on IV antibiotics
- Length of time on oral antibiotics
- Total length of time on antibiotics
- Length of time from presentation to discharge
- Blood tests carried out and their results
- Antibiotics prescribed (during hospital stay and at discharge)
- Dosage (Normal / High as defined in Children's British National Formulary)
- Adherence to discharge prescription
- Reasons for non-adherence or changes to prescribed regimes.

Complications / Failure of treatment

- Complication types
- Actions arising from complications
- Treatment failure (Y/N)

Analysis

The primary interest are the sub-group of children with acute SA / OM and no chronic comorbidities (simple cases). All analyses described below will therefore be carried out for this sub-group in the first instance. The other two sub-groups (chronic SA/OM and infections arising from previous orthopaedic surgery) will be analysed separately as a secondary analysis. See *Appendix A: Template Results Tables* for tables referred to in the following analysis plan.

Objective 1

- [1A] See Section 8.2 above for demography and definition of diagnosis groups. Numbers and percentages will be calculated and results tabulated separately for: demographics; diagnosis groups; presentation; history of orthopaedic surgery; medical history; and antibiotics prescribed prior to presentation. See Tables 1A-1,2,3,4,5,6 below
- [1B] The clinical time-line from first presentation through to diagnosis will be explored. Time to hospital referral, first imaging, surgery, radiological diagnosis, and initiation of IV antibiotics will all be summarised using appropriate descriptive statistics [see Table 1B-1].
- [1C] The number and percentage of cases undergoing different types of surgery prior to diagnosis will be reported [see Table 1C-1].
- [1D] The number and percentage of cases testing positive for at least one micro-organism, and each of 8 unique micro-organisms will be reported, split by centre type (Tertiary / Secondary). Any other micro-organisms detected will be categorised and reported as “Other”. Of cultures testing positive for *Staphylococcus aureus*, the number and percentage where PVL is tested for will be reported. The number and percentage of cases where a PCR test is also carried out will be calculated by centre type. [See Table 1D-1].

The number and percentage of types of sample for micro-biological testing (e.g. blood, pus, etc.) that are typically taken from children will be reported [see Table 1D-2].
- [1E] The number and percentage of cases with test results at presentation for: each of 6 blood tests; and the combinations ‘CRP & ESR’ and ‘CRP & no ESR’ will be reported, split by centre type (Tertiary / Secondary) [see Table 1E-1]. A boxplot for each of the six blood test measures at presentation will be created to show the distribution of results. Proportions with elevated results (above centre-specific normal ranges) will be calculated for each blood test type [see Table 1E-2].

The blood test result ‘CRP_{max}’ will be summarised for culture-positive and culture negative cases and a box plot created to compare these. This analysis will be split by age-group. This is to explore whether a higher CRP_{max} is associated with particular organisms. Differences that are clinically significant will be tested for statistical significance using appropriate hypothesis tests [see Table 1E-3].
- [1F] There are five imaging methods that could be requested by clinicians to aid diagnosis. The number and percentage of cases for each imaging type used prior to diagnosis will be reported, split by centre type (Tertiary / Secondary) and of these the number and percentage abnormal [see Table 1F-1].

Objective 2

Treatment of children with SA or OM takes the form of antibiotic treatment and additionally for some cases, surgical intervention. Initially antibiotics are given intravenously. At a later date, antibiotics are given orally – the timing of the switch is based on clinical judgement that the child has recovered sufficiently and is capable of taking drugs orally.

- [2A] The lengths of time on IV antibiotics, oral antibiotics, and total antibiotic duration will be summarised using appropriate descriptive statistics. (Note that these times are based on what happened during hospital stay and what was **planned** at discharge. It is not possible to obtain data for the actual date when antibiotics were stopped post discharge.) Results will also be split by centre type, whether there was at least one surgical procedure after initiation of IV antibiotics, if CRP_{max} occurred at presentation, and by microbes detected. [See Table 2A-1].

Antibiotic regimes will be further summarised for the sample: Number of antibiotics given in the initial treatment; timing of oral switch (<1 wk, 1-2 wks and >2 wks)); total course of antibiotics (shortened vs standard); dose (augmented at least once vs standard dose throughout where ‘augmented at least once’ is defined as having at least one high dose of IV antibiotics); and total number of different antibiotics prescribed over the full treatment period [see Table 2A-2].

- [2B] Antibiotics prescribed during hospital stay will be summarised using frequencies and percentages. There are a large number of antibiotics that could be prescribed by either route. Of these, 4 named IV antibiotics and 5 named oral antibiotics are of particular interest. A category labelled ‘other’ will be used to define all other antibiotics given by each route. For each antibiotic and route, summary statistics will be reported for whether it was part of the initial prescription; given at least once; frequency of administration of doses during a day; daily dose per kg weight of child; and duration of course (> 1 week Y/N). This will give an overview of the most commonly prescribed antibiotics during hospital stay [see Table 2B-1].

Initial IV antibiotic prescriptions will be compared between secondary and tertiary site types; between children with and without penicillin allergy; and with and without sickle cell disease [see Table 2B-2].

- [2C] Blood test results are routinely used to aid the decision to stop giving antibiotics via IV (ie. oral switch). The combinations of blood tests carried out immediately prior to (on the day before or on the day of) the oral switch will be reported as numbers and percentages. CRP as a proportion of CRP_{max} will be summarised [see Table 2C-1].

The change in blood test results over time will be explored graphically using boxplots. For each blood test type, a plot will be produced showing the distribution of results at: presentation; initial of IV; and on each day following start of IV.

- [2D] The number and percentage of cases undergoing different types of surgery post diagnosis will be reported [see Table 2D-1].
- [2E] Appropriate summary statistics will be used to describe length of hospital stay for cases – overall, and split by age-group and centre type [see Table 2E-1].
- [2F] The number and percentage of cases with imaging after initiation of IV will be reported split by site type and image type, with results given.
- [2G] Antibiotics prescribed at discharge will be summarised using frequencies and percentages. There are a large number of antibiotics that could be prescribed by either

route. Of these, 4 named IV antibiotics and 5 named oral antibiotics are of particular interest. A category labelled ‘other’ will be used to define all other antibiotics given by each route. For each antibiotic and route, summary statistics will be reported for whether it was given at least once; daily dose per kg weight of child; and planned duration of course. This will give an overview of the most commonly planned antibiotic regimes at discharge [see Table 2F-1].

[2H] Antibiotic regimes post discharge are not always adhered to. The number and percentage of those stopped early will be reported, split by who took the decision (Parent / Hospital / GP). In the same way the number and percentage of patients who had a change to the planned regime will be reported split by who made the change (Hospital / GP). The frequencies of 5 possible reasons for shortening or changing regime will be explored [see Table 2G-1].

Objective 3

[3A] The number and percentages of cases experiencing a complication of any kind will be reported. These will be further split by ‘Complication Type’, and cross-tabulated with ‘Action Taken’ (None / Surgery / Change of antibiotic regime / Re-admission to hospital / Other) [see Table 3A-1].

[3B] Treatment failure is determined by complications that result in certain actions. e.g. Surgery. The outcomes ‘Treatment Failure’ (Y/N) and ‘Any Complication’ (Y/N) will be cross-tabulated with three antibiotic regime variables: Timing of oral switch (Early / Standard); Total course of antibiotics (Shortened / Standard); and Overall dose (High / Normal). Associations between regime types and outcomes will be measured using odds-ratios and 95% CIs. This will give an overview of whether treatment failure and complications may be more likely for certain types of regime [see Table 3B-1].

[3C] Treatment Failure (Y/N) and Any Complication (Y/N) will be cross-tabulated with surgery undertaken (limited to surgery post presentation). Associations between surgery types and outcomes will be measured using odds-ratios and 95% CIs. This will give an overview of whether treatment failure and complications may be more likely for certain types of surgery [see Table 3C-1].

Analyses of missing data / withdrawals

As this is a service evaluation, there should be only a small number of withdrawals. Those that do occur will be documented. It may be of importance if withdrawals are clustered by centre.

Missing data will be noted and wherever possible, the reasons reported. If a large amount of data critical to the analysis are missing, some changes to the analysis plan may be needed.

Setting results in context of previous research

Once the service evaluation has been completed the results will be set in context of the existing evidence base.

References

2. ICH E3 chapter 12.

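### Objectives 1 and 2 ask about osteomyelitis, but the diagnosis and antibiotic-duration results are planned only for osteomyelitis and septic arthritis pooled

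*SAP*

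**What the plan says.** In the SAP section Study Objectives, Objective 1 asks "What are the clinical, biochemical and radiological criteria used by UK paediatricians / orthopaedic surgeons / radiologists to diagnose osteomyelitis" and Objective 2 asks "What is the range of durations of intravenous and oral antibiotics used to treat osteomyelitis". Appendix A repeats the Objective 2 question as the heading over Table 2A-1. Objective 3 names no disease; it opens "What are the rates of treatment failures / complications for different" and goes on to antibiotic regimes and surgery types.

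The rest of the SAP covers both diseases. The first aim is "Assess current case load, disease spectrum & clinical practice in the diagnosis & treatment of OM/SA in secondary & tertiary UK care". The inclusion criterion begins "All children from birth to 16 years with a clinical diagnosis of osteomyelitis or septic arthritis admitted to participating hospitals from home". The Analysis section sets the main analysis population with "The primary interest are the sub-group of children with acute SA / OM and no chronic comorbidities (simple cases" and applies it to every analysis that follows. The Objective 2 analysis opens "Treatment of children with SA or OM takes the form of antibiotic treatment".

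For antibiotic durations, item [2A] says "Results will also be split by centre type, whether there was at least one surgical procedure after initiation of IV antibiotics", then adds whether the maximum CRP occurred at presentation, and the microbes detected. Disease type is not in that list.

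**The concern.** Someone who takes Objectives 1 and 2 at their word will look for the diagnostic work-up and treatment durations of children with OM. The plan produces neither. The results for simple cases mix two diseases, and the pooled figures cannot be separated afterwards from the published tables.

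The second aim of the evaluation is to judge whether a randomised trial of shorter intravenous therapy is feasible, so the duration summaries are likely to be read as current practice. If clinicians treat OM and SA for different lengths of time, a pooled summary depends on how many of each were accrued. The comparisons of tertiary with secondary centres would carry the same dependence, since the two centre types may see different proportions of OM.

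**Working it through.** **Does any planned output give an OM result?** Taking the SAP in order:

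- Study Objectives: OM alone in Objectives 1 and 2; no disease named in Objective 3.
- Analysis: all analyses are first run in simple cases, OM and SA together. The secondary analyses take chronic disease and infection after orthopaedic surgery, not OM against SA.
- Analysis, [2A]: four splits (centre type, surgery after the start of intravenous therapy, timing of maximum CRP, microbes). None is disease type.
- Appendix A: Table 1A-2 has OM and SA rows under Simple and under Complex, and these are counts of cases. Template tables 1B to 1G, 2A to 2H and 3A to 3C have no OM or SA row or column.
- Data Collection: type and site of disease are recorded, so a split needs no new data.

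The answer is no. Only the number of OM cases would be known.

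**How far could pooling move a duration?** The SAP has no figure to reproduce, so every value here is an assumption. Let w be the OM share and let the mean total course be 42 days in OM and 28 days in SA.

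Pooled mean = 42w + 28(1 − w)

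- w = 0.40: 16.8 + 16.8 = 33.6 days, which is 8.4 below the OM value.
- w = 0.70: 29.4 + 8.4 = 37.8 days, which is 4.2 below the OM value.

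Two centre types with the same practice but these two mixes would differ by 14 × (0.70 − 0.40) = 4.2 days. In general the spurious difference is the between-disease difference times the difference in mix, so it is zero if either is zero. The sum uses means; a median would also shift, but not by this formula.

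**Could disease type affect the odds ratios in 3B?** Assume a 50:50 mix, 30% of OM and 70% of SA under 6 weeks, failure of 10% in OM and 5% in SA, and no effect of course length within either disease. As fractions of all cases:

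- Shortened, failed: 0.5×0.3×0.10 + 0.5×0.7×0.05 = 0.0325; not failed: 0.4675.
- Standard, failed: 0.5×0.7×0.10 + 0.5×0.3×0.05 = 0.0425; not failed: 0.4575.
- Crude odds ratio = (0.0325/0.4675) / (0.0425/0.4575) = 0.75.

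With SA failure of 3% it is 0.63. With equal failure of 8% in both diseases it is 1.00.

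**What does splitting cost in precision?** The SAP expects at least 500 cases. The worst-case 95% half-width for a proportion is 1.96 × √(0.25/n):

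| Group | n | Half-width (percentage points) |
|---|---|---|
| Pooled | 500 | 4.4 |
| OM at an assumed 70% | 350 | 5.2 |
| OM at an assumed 50% | 250 | 6.2 |
| OM at an assumed 30% | 150 | 8.0 |

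These treat all 500 as analysed. Simple cases will be fewer, so the real intervals will be wider.

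**The case against.** The strongest reply is that Objectives 1 and 2 are loosely worded and the analysis is as intended. The aim, the design, the inclusion criteria and the main analysis population all cover both diseases. The Study Outcomes section speaks of children with SA or OM and then assigns diagnosis to Objective 1 and treatment to Objective 2. The future trial concerns bone and joint infections generally, and the [2A] splits include the kinds of factor that Objective 2 itself names: surgery, blood tests and microbiology. Much of this stands. Rewording would remove the contradiction, and a pooled summary is a legitimate result for that wider population. It would not show whether practice differs by disease, which a study that sets out to describe the disease spectrum and clinical practice can report at little cost.

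A reader might go further and infer three things that the SAP does not support:

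- That pooling the outcomes contradicts the objectives. Objective 3 names no disease, so it does not.
- That the 3B odds ratios are confounded by disease type. Nothing in the SAP says that failure rates or course lengths differ between OM and SA, and with equal failure rates the illustration gives 1.00. The SAP also presents these tables as an overview within a descriptive study.
- That pooled durations are wrong by some number of days. The day figures rest wholly on assumed means and mixes.

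It is also fair to object that stratifying 3C would fail in practice. Thirteen surgery types by two outcomes already give 26 odds ratios; splitting by two diseases makes 52, many of them likely to rest on very few events.

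**Conclusion.** The mismatch is real and rests on the text alone: Objectives 1 and 2 and the heading over Table 2A-1 ask about OM, and no planned diagnosis or duration output is specific to OM. Loose wording is a plausible cause, so this does not show that the pooled analysis is mistaken.

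The dependence of pooled durations and centre-type comparisons on case mix is conditional. It needs practice to differ by disease and, for the centre comparison, the mix to differ as well. The SAP gives neither quantity, so the effect runs from nil upwards and 4.2 days is only an example. Confounding in 3B is possible but not demonstrated. For a descriptive study this is a change that should be made before analysis because it is cheap and lets the study answer its own questions; it does not threaten the study's validity.

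**What to change.** 1. Keep the pooled columns and add OM and SA columns, with a column for both where that is recorded, to the main diagnosis and duration tables in Appendix A: 1B-1, 1E-1, 1G-1, 2A-1, 2A-2 and 2E-1.
2. Decide what Objectives 1 and 2 mean. If both diseases are intended, reword the two objectives and the heading over Table 2A-1 to say OM and SA. If OM is intended, point to the OM columns as the answer.
3. For 3B, show the cross-tabulations by disease type, or adjust the odds ratios for it, and describe this as a check.
4. Do not require the same for each surgery type in 3C, where cells would be sparse.

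The cost is extra table columns; disease type is already in the database. The downside is smaller cells and wider intervals, for example a half-width of 6.2 instead of 4.4 percentage points if half of 500 cases were OM.
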